6.1 Additional definitions

Definitions of the Mayo classification and surgical approach classification systems that should be used to define improvement are shown below:

Mayo classification (levels are ordered by increasing extensiveness):

- Level 0: thrombus limited to the renal vein
- Level 1: into IVC <2cm from renal vein ostium level
- Level 2: IVC extension >2cm from renal vein ostium and below hepatic vein
- Level 3: thrombus at the level of or above the hepatic veins but below the diaphragm
- Level 4: thrombus extending above the diaphragm.

Tumour thrombus surgical management approach classification (approaches are ordered by increasing invasiveness):

1. Thrombus - Milked back into renal vein and side clamped
2. Infra-hepatic (IVC clamping with no liver mobilisation)
3. Retro-hepatic (liver mobilisation and clamping below hepatic veins)
4. Retro-hepatic (liver mobilisation and clamping above hepatic veins)
5. Supra-hepatic (infradiaphragmatic)

6. Supra-hepatic (supradiaphragmatic)

Note that efficacy outcomes can be expressed as a percentage of the ITT population or the evaluable population (meaning that the denominator should change to be either the size of the relevant population).

7 Tabulations, Figures and Listings

This section is the complete operational specification for the statistical analysis and subsequent presentation of that analysis for the lifetime of this trial. Throughout this section, tabulations consist of counts and percentages per category unless stated otherwise. Listings will include the patient identifier and the specific data for that listing.

7.1 Study Recruitment (ITT population)

- Plot of actual cumulative recruitment against time since study opened will be provided; target recruitment rate line will be superimposed on this plot.
- Table of recruitment by centre showing the date the centre opened, the date the first and last patients were recruited and the number recruited. Centres that have opened but not recruited patients will be included in this table.

7.2 Eligibility/Population membership (ITT population)

- Numbers of patients in each population ([Sections 4.2](#) and [4.3](#)) will be presented.
- Ineligible patients will be listed along with the reason for their ineligibility.
- Patients who are recruited but do not receive any treatment will be listed with reasons for not treating.

7.3 Baseline data and demographic characteristics (ITT population)

Discrete variables will be summarised by frequencies and percentages. For continuous variables medians, inter-quartile ranges and ranges will be presented and where appropriate, the results will be presented in suitable categories:

- Registering centre
- Age at registration
- Karnofsky Performance status (ECOG)
- Other medical conditions (frequency and list), with specific reference to cardiovascular, cerebrovascular, thromboembolic, respiratory, gastrointestinal, endocrine/metabolic,

neurological conditions (further specification of “Other” reasons will be listed). Existing allergies should also be included and specified.

- Heart rate, respiratory rate, systolic and diastolic blood pressure
- Height, Weight, BMI
- Pregnancy test (conducted and result)
- Existing signs and symptoms (with CTCAE gradings)
- Laboratory investigations, including full blood count; white blood cell count; serum biochemistry; thyroid function; urinalysis
- Previous diagnosis of other cancer
- Renal Cell Carcinoma histological type (including whether predominantly clear cell)
- Tumour data, including staging (TNM status); grading (ISUP/Furman); MSKCC model and risk; IMDC model and prognosis
- Surgical assessment data, including whether patient is surgically resectable; whether radiotherapy has been given
- Lesion data: number of target and non-target lesions; sums of longest target lesions diameters
- Thrombus data: IVC and/or MRV involvement; relevant measurements (see [Section 6](#))
- Mayo classification

7.4 Delivery of study therapy (evaluable population)

- Total dose (mg) taken per patient separately for axitinib (median, IQ range and range)
- Total dose (mg) missed per patient separately for axitinib (median, IQ range and range)
- Percentage of intended dose taken per patient (taken/(taken+missed)) separately for axitinib (median, IQ range and range)
- Reasons for missed doses will be tabulated; further specification of “other” reasons will be listed.
- The number of dose reductions per patient
- The number of dose escalations per patient
- Reasons why axitinib was reduced to 3mg BID
- Reasons why axitinib was reduced to 2mg BID
- Reasons for stopping trial drug will be tabulated; “other” reasons and “Adverse event/toxicity” reasons will be listed

7.5 Safety Analysis

7.5.1 To inform early stopping rule (1) (Section (1)5) (ITT population)

A listing of:

- Patient label
- Staging (M) data at screening
- Date of Surgery
- Flag indicating whether surgery took place
- Whether the patient belongs to the evaluable population
- Relevant patient notes including any reasons that surgery was not performed or staging has not been provided

7.5.2 To inform early stopping rule (2) (Section 5) (ITT population)

A listing of:

- Patient label
- Staging (M) data at screening
- Flag indicating whether surgery took place
- Staging (M) data at surgery
- Whether the patient belongs to the evaluable population
- Relevant patient notes including any reasons that surgery was not performed or staging has not been provided

7.5.3 To inform early stopping rule (3) (Section 5) (ITT population)

A listing of:

- Patient label
- Mayo classification at screening
- Mayo classification at week 3
- Mayo classification at week 9
- Flag indicating whether surgery took place
- Details of all patients with extension of their VTT will be presented including the planned surgery and procedure performed.

7.5.4 Toxicities (including adverse events and laboratory values) (Safety population)

- All adverse events will be coded according to the CTC toxicity criteria and the worst value over the study drug periods determined for each patient.
- Laboratory values will be coded according to the CTC toxicity criteria and the worst value over the study period determined for each patient.
- Any adverse events or laboratory anomalies which are graded \geq grade 1 by at least 10% of patients will be tabulated.
- Details of toxicities will be summarised to show (i) grade at trial entry; (ii) the highest grade over the course of treatment; and (iii) the highest grade in follow up. For any toxicity graded \geq grade 2 at any timepoint, the toxicity grading will be tracked over the course of the trial in a graphical form.

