### **Final Analysis**

The final analysis will be performed once the end of study has been declared and will include summaries of the % of evaluable patient with improvement in the Mayo classification; % change in surgical approach; the response rates as determined by RECIST criteria V1.1 and an evaluation of morbidity utilising the Clavien-Dindo classification system.

The dose of axitinib delivered will be summarised with the median and range of total dose being presented. Adverse events will be classified using CTCAE V4 and the worst grade for each toxicity will be summarised.

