4.1 Sample Size Calculations and recruitment schedule

The aim is to recruit 20 patients over a 24 month period. A Simon two stage minimax design to distinguish a <5% from a >25% improvement in the Mayo classification requires 20 evaluable patients (90% power, 10% 1-sided).

Thirteen patients would be recruited in the first stage. If no patients demonstrate an improvement in their Mayo classification between screening and week 9, accrual to the clinical trial would stop (see [Section 3.1.2](#)). If one or more patients demonstrate an improvement in the Mayo classification between screening and week 9, a further seven patients would be recruited (to the final total of 20 evaluable patients). In order for the clinical trial to be considered a success, at least three evaluable patients should demonstrate an improvement in disease or treatment between screening and week 9 (see [Section 7.6.1](#)).

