4.4 Safety Population

The safety population includes all patients in the ITT population who have received at least one dose of the study drug (including any patients who were enrolled in error, received study drug and were subsequently found to be ineligible). In this study, this population is equivalent to the evaluable population.

5 Safety Evaluations

The study will use the following safety parameters.

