5.1 Adverse events, SAEs and SUSARs

All reported adverse events (including adverse reactions, SAEs and SUSARs) will be presented, with events categorised against the National Cancer Institute Common Terminology Criteria for Adverse Events v4.0.

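### SAP 7.5.4 gives no table row to a severe, non-serious toxicity confined to one patient, and leaves the window for worst laboratory grades undefined

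*SAP*

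**What the plan says.** SAP 7.5.4 covers adverse events and laboratory values together, in the safety population. It has four parts that matter here.

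- Adverse events are coded by CTC grade and the worst value is taken over the *study drug periods*.
- For laboratory values the window is worded differently: "Laboratory values will be coded according to the CTC toxicity criteria and the worst value over the study period determined for each patient". The SAP does not define *study period*.
- The table is restricted by frequency. Events or laboratory anomalies at or above "grade 1 by at least 10% of patients will be tabulated". No separate rule is given for higher grades.
- Details of toxicities are summarised by grade at entry, highest grade on treatment and highest grade in follow-up. Any toxicity reaching grade 2 or above at any time is also graphed. Neither output carries a stated frequency limit.

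Two other places promise more than the filtered table gives. Protocol 9.2 (Final Analysis) says that "the worst grade for each toxicity will be summarised". SAP 5.1 says: "All reported adverse events (including adverse reactions, SAEs and SUSARs) will be presented". The opening of SAP 7 says of itself: "This section is the complete operational specification for the statistical analysis". SAP 7.5.5 sends serious events and SUSARs to a separate output from the pharmacovigilance database.

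**The concern.** The filter counts patients with any grade of a toxicity and ignores how severe the toxicity was. In a trial of 20, a 10% cut-off removes every toxicity that only one patient had. A grade 4 laboratory abnormality in one patient is then treated like a single grade 1 complaint.

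SAP 5.1 promises that everything is presented. But SAP 7 claims to be the full operational specification, and it contains no all-events table and no listing of non-serious events. A programmer working from SAP 7 would apply the filter. Protocol 7.2 sends only related reactions to the case report form, so a non-serious event left out would usually be one already judged related.

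The laboratory window raises a second, smaller question. If the worst value may come from bloods taken after a kidney has been removed, a post-surgical creatinine or haemoglobin grade could become a patient's worst grade and count towards the 10%.

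Protocol 1.5 names adverse events that affect fitness for surgery as a risk of the eight weeks of axitinib, and Protocol 13 asks the DMC to look at toxicities. Counts of severe toxicity by grade are what that judgement needs.

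**Working it through.** **1. Denominator.** SAP 4.4 sets it: "The safety population includes all patients in the ITT population who have received at least one dose of the study drug". The planned number is 20, with 13 at the interim (SAP 4.1). The design is "A Simon two stage minimax design to distinguish a <5% from a >25% improvement in the Mayo classification", with 10% one-sided error and 90% power. The rule is to stop if 0 of 13 improve and to call the trial positive if at least 3 of 20 do. The chance of a positive result is the sum over x ≥ 1 of P(X₁ = x) × P(X₂ ≥ 3 − x), with X₁ ~ Bin(13, p) and X₂ ~ Bin(7, p).

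- p = 0.05: 0.0736 (limit 0.10)
- p = 0.25: 0.903 (target 0.90)

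A search over two-stage designs returns 20 in total with 13 in the first stage, so the plan's figure is reproduced.

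**2. What 10% means in patients.** The filter needs the smallest k with k/n ≥ 0.10.

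- n = 20: 1/20 = 5.0%, 2/20 = 10.0%, so k = 2.
- n = 13: 1/13 = 7.7%, 2/13 = 15.4%, so k = 2.
- n = 21, if one extra patient were treated: 2/21 = 9.5%, so k = 3, and a toxicity seen in two patients would also be left out.

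**3. How often a toxicity falls in exactly one patient.** The documents give no expected rates for this trial, so the any-grade risks p below are assumptions. P(X = 1) = n p (1 − p)^(n−1). For example, at n = 20 and p = 0.05 it is 20 × 0.05 × 0.95^19 = 0.377. The conditional figure divides by P(X ≥ 1) = 1 − (1 − p)^n.

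| Assumed any-grade risk | n = 20: exactly one | n = 20: no row, given it occurs | n = 13: exactly one | n = 13: no row, given it occurs |
|---|---|---|---|---|
| 2% | 27.2% | 82.0% | 20.4% | 88.3% |
| 5% | 37.7% | 58.8% | 35.1% | 72.2% |
| 10% | 27.0% | 30.8% | 36.7% | 49.2% |

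Two rates from Protocol 1.4.1, both from the cytokine-refractory study, show the contrast.

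- Treatment-related proteinuria, 4/52 = 7.7%: P(exactly one of 20) = 20 × 0.0769 × 0.9231^19 = 33.6%.
- Axitinib-induced hypertension, 30/52 = 57.7%: 20 × 0.577 × 0.423^19, about 9 × 10⁻⁷, effectively zero.

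**4. Where a non-serious grade 3-4 toxicity in one patient would appear.**

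| Output | Would it appear? |
|---|---|
| 10% table (SAP 7.5.4) | No |
| Entry/treatment/follow-up summary (SAP 7.5.4) | Unclear: the text does not say whether the filter applies |
| Graph of grade 2 or higher (SAP 7.5.4) | Yes, with no frequency limit |
| Serious event output (SAP 7.5.5) | No, as it is not serious |
| Presentation of all events (SAP 5.1) | Promised, but SAP 7 specifies no output for it |

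**5. Laboratory window.** Protocol 5.2.9 and 5.2.10 schedule blood counts, renal and liver function at 6 and 12 weeks after surgery. Protocol 9.3 ends the study after the 12-week visit. Read naturally, *study period* therefore includes both samples, while *study drug periods* for adverse events does not. The entry/treatment/follow-up split separates most of these values. It does not say which window feeds the overall worst value and the 10% count, or which phase holds a sample taken between stopping drug and surgery. The documents give no basis for sizing any distortion.

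**The case against.** The strongest reply is that SAP 7.5.4 should be read as a whole. A frequency-filtered main table is common, and here it sits beside two outputs with no stated filter. The entry/treatment/follow-up summary covers toxicities, which the section heading says include laboratory values, and it comes close to what Protocol 9.2 promises. The grade 2 or higher graph shows any severe toxicity. Serious events have their own output, and the stopping rules have their own listings in SAP 7.5.1 to 7.5.3.

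Much of this stands, and it rules out three stronger readings.

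- *A severe event in one patient disappears from the report.* The documents do not support this. It has no row in one table, but the graph still shows it.
- *Surgical changes are mixed into axitinib toxicity.* This goes too far. The phase split already separates most post-surgical laboratory grades from on-treatment grades, and the inclusion of post-surgical bloods in *study period* is an inference from an undefined term.
- *There is a 37.7% chance of losing a severe event.* The figure concerns a toxicity with an assumed 5% any-grade risk. It counts a lone grade 1 event equally. A severe event misses the table only if no other patient has that toxicity at any grade, so a common toxicity such as hypertension would be tabulated.

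What the reply does not settle is whether the unfiltered-looking summary inherits the filter stated in the bullet just before it. A graph also does not give a count by grade.

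**Conclusion.** The point holds, and it is minor. The stated tabulation rule ignores severity, so at 20 or 13 patients a non-serious grade 3-4 toxicity seen in one patient has no row in the SAP 7.5.4 table. The remaining outputs do not clearly deliver what Protocol 9.2 and SAP 5.1 promise. For any-grade risks of 2% to 10%, roughly 27% to 38% of such toxicities would occur in exactly one of 20 patients. This rests on assumed rates, independence between patients and a safety population of exactly 20.

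The laboratory window is a secondary ambiguity. It matters only for the overall worst laboratory grade and the 10% count, and it depends on reading *study period* as running to the 12-week visit.

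Both parts concern how safety is reported.

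**What to change.** Change SAP 7.5.4 as follows.

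1. Apply the 10% filter only to toxicities with no occurrence at grade 3 or higher. Tabulate every adverse event and laboratory abnormality of grade 3 or higher by grade, whatever its frequency.
2. State that the worst laboratory grade used for the 10% count is the highest on-study grade before surgery. This also places samples taken between stopping drug and surgery. Show the highest post-surgery grade only in the existing follow-up column. For patients never operated on, name the date on which the window closes.
3. Say whether the entry/treatment/follow-up summary covers all toxicities or only those that pass the filter.

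The cost is a short SAP wording change and a few more table rows. No extra data are needed.

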7.5.5 Serious Adverse Events/Reactions and SUSARs (ITT population)

- Details of serious adverse events/reactions and SUSARs will be provided in a separate document output from the SCTRU's pharmacovigilance database.

7.6 Efficacy analysis (evaluable and ITT populations)

Note that these analyses will be carried out for both the evaluable and ITT populations. This represents a sensitivity analysis that assesses whether results are robust in the ITT population.

7.6.1 Primary endpoints

NB. For all primary endpoint assessments, if a patient does not have a week 9 scan, then their week 3 scan (if available) should be used instead.

7.6.1.1 For patients presenting at screening with a Mayo Classification of Level 1 or above

- The number and percentage of patients with an improvement in the Mayo Classification between screening and week 9 (see [Section 6.1](#) for Mayo classification system).
- The number and percentage of patients with no change in the Mayo Classification between screening and week 9 (see [Section 6.1](#) for Mayo classification system).
- The number and percentage of patients with deterioration in the Mayo Classification between screening and week 9 (see [Section 6.1](#) for Mayo classification system).

7.6.1.2 For patients presenting at screening with a Mayo Classification of Level 0

- The number and percentage of patients demonstrating improvement in status, i.e.:

- For patients presenting with right renal vein tumour thrombus: a change of tumour thrombus from main renal vein to branches of the renal vein between screening and week 9.
- For patients presenting with left renal vein tumour thrombus: a change of tumour thrombus from the main renal vein between screening and week 9 as follows:
 - If the patient is lateral to the gonadal vein at screening, a change from the main renal vein into the segmental veins
 - If the patient is medial to the gonadal vein at screening, a change from the main renal vein medial to the gonadal vein to the renal vein lateral to the gonadal vein
- The number and percentage of patients with no change in tumour thrombus status (i.e., tumour still present in the main renal vein and medial to the gonadal vein (on left side)) between screening and week 9.
- The number and percentage of patients demonstrating an extension of the thrombus into the inferior vena cava between screening and week 9.

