## **4. TREATMENT**

### **4.1. Treatment Schedule**

Patients should start axitinib treatment on day 1, week 1 of the study and continue for 8 weeks.

Patients will be prescribed 1 pack (28 tablets) of 5mg BID at week 1. Patients will then be prescribed further axitinib every 2 weeks following the dose modification schedule detailed in

section 4.2 (depending on toxicities and blood pressure). Doses should be taken appropriately 12 hours apart and patients should be instructed to take their doses at approximately the same time each day with or without food as per instruction. On clinic days only, patients will be advised to fast for 6 hours prior to their clinic visit.

Patients should be advised to stop axitinib treatment a minimum of 36 hours and maximum of 7 days prior to week 9 surgery and tissue collection.

If a patient vomits or misses a dose, an additional dose should not be taken. The next prescribed dose should be taken at the usual time. If the patient reports having missed a dose or vomiting, this should be recorded in the source documents and case report forms (CRFs).

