#### Dose Interruption and Reduction

Patients experiencing non-haematological drug reactions greater than CTCAE Grade 2 or haematological reactions greater than CTCAE Grade 3 should undergo dose modification. The current version of the Summary of Product Characteristics (SmPC) should be used to assess whether any adverse event is attributable to the drug.

Axitinib should be stopped in the event of significant toxicity and restarted if appropriate when toxicities have resolved. If the patient has had an interruption of axitinib more than 2 weeks, it must be discussed with the Chief Investigator (CI) before the patient restarts study drug.

Patients permanently removed from treatment for intolerable toxicity should receive a post treatment CT scan assessed according to RECIST 1.1 criteria, and should revert to standard of care.

The criteria for dose modification for axitinib related adverse events are summarised in the table below:

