## **9. STATISTICS**

### **9.1. Sample Size**

The aim is to recruit 20 patients over a 24 month period. A Simon two stage minimax design to distinguish a <5% from a >25% improvement in the Mayo classification requires 20 patients (90% power, 10% 1-sided). Thirteen patients would be recruited at first stage; if at least 1 patient had an improvement in the Mayo classification a further 7 patients would be recruited (to the final total of 20 patients).

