### **9.2. Analysis Plan**

The main analysis will be conducted on the “as-treated” population. All patients who receive study drug will be included in the interim and final analysis. Any patient who withdraws from the study prior to receiving drug will not be included in the analysis. At least 3 patients showing a reduction in Mayo Classification would produce a positive trial.

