1.1 Primary endpoint

The primary end-point for this study is the percentage of evaluable patients with an improvement in disease as a result of taking the study drug. The definition of an improvement will vary according to the patient's Mayo Level as captured at screening:

- **For patients presenting at screening with a Mayo Classification of Level 1 or above**, an improvement in disease will be represented by a reduction in their Mayo Classification at week 9.
- **For patients presenting at screening with a Mayo Classification of Level 0**, an improvement in disease will be represented by either:
 - a change of tumor thrombus from main renal vein to branches of the renal vein (on the right);
or
 - a change of tumor thrombus from main renal vein to the renal vein lateral to the gonadal vein (on the left).

See [Section 6.1](#) for further details regarding the definition of improvement in relation to the Mayo classification and the surgical approach classification.

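### A missing week-9 scan is replaced by the week-3 scan, so an improvement seen about 14 days into an 8-week course counts in full towards the three successes needed, and no planned analysis tests this

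*SAP*

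**What the plan says.** SAP 1.1 sets the time point. For patients at Mayo level 1 or above, "an improvement in disease will be represented by a reduction in their Mayo Classification at week 9". SAP 7.6.1.2 uses the same interval, screening to week 9, for the sub-level criterion at level 0, and SAP 4.1 uses it for the success rule.

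SAP 7.6.1 then adds a note covering all primary endpoint assessments: "if a patient does not have a week 9 scan, then their week 3 scan (if available) should be used instead". It names no other scan. The statistics section of the protocol (9.1 to 9.2) has no such fallback.

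On the course itself, Protocol 4.1 says: "Patients should start axitinib treatment on day 1, week 1 of the study and continue for 8 weeks". Protocol 5.2.4 places the week-3 visit, with an abdominal MRI for all patients, at day 1 of week 3, within 7 days.

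Protocol 4.2 (Dose Interruption and Reduction) says that patients permanently removed for intolerable toxicity "should receive a post treatment CT scan assessed according to RECIST 1.1 criteria". It fixes no date and asks for no Mayo reading. The SAP does not mention this scan.

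The verdict rests on a small count. Protocol 9.2: "At least 3 patients showing a reduction in Mayo Classification would produce a positive trial". SAP 4.3 needs only one dose for a patient to be evaluable, so patients who stop early stay in the primary analysis.

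**The concern.** Week 3 is a different time point from the one that defines the endpoint. It comes about 14 days after the first dose, at the first visit where the dose can be raised, so the scan reflects the starting dose or less. Protocol 1.5 justifies 8 weeks of treatment by an earlier study in which the maximum effect on the primary tumour was seen by 7 weeks. A reduction in level at week 3 may not last to surgery, yet it scores the same as one present at week 9.

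The fallback also takes the older scan where a newer one exists. A patient removed for toxicity after the week-3 scan may have a later CT, and Protocol 5.2.11 names CT, with MRI, as a source for Mayo level.

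The planned check does not reach this rule. SAP 7.6 says of the ITT analysis: "This represents a sensitivity analysis that assesses whether results are robust in the ITT population". According to SAP 3.1.4 and 6.1, that analysis changes the denominator. It adds registered patients who took no drug and leaves every week-3 success in the numerator.

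At stake is the positive or negative verdict, which one reading can decide. SAP 3.1.2 refers the futility decision to 7.6.1 as well, so a single week-3 improvement could also carry the trial past its interim look.

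**Working it through.** **Inputs from the documents.** Protocol 9.1 and 9.2: 13 patients, then 7 more if at least 1 improves; success at 3 or more of 20; rates of 5% and 25%; power 90%; one-sided error 10%.

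**Assumptions.** *m* is the number of evaluable patients scored on week 3, and *q* is the chance that each shows a week-3 improvement. The documents give neither, so both are varied.

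**Step 1: reproduce the design.** P(positive) = P(X1=1)·P(X2≥2) + P(X1=2)·P(X2≥1) + P(X1≥3), with X1 ~ Bin(13, p) and X2 ~ Bin(7, p).

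- p = 5%: 0.3512×0.0444 + 0.1109×0.3017 + 0.0245 = 0.0736
- p = 25%: 0.1029×0.5551 + 0.2059×0.8665 + 0.6674 = 0.9030

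A search over all two-stage rules confirms this as the minimax design. The plan's figures reproduce: error 7.4%, power 90.3%.

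**Step 2: put three patients on the fallback.** Take two in stage 1 and one in stage 2. Then X1 = Bin(11, 5%) + Bin(2, q) and X2 = Bin(6, 5%) + Bin(1, q), in the same formula.

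- q = 0 (counted as not improved): 0.3293×0.0328 + 0.0867×0.2649 + 0.0152 = 0.049
- q = 5%: back to the Step 1 case, 0.074
- q = 10%: 0.3691×0.0560 + 0.1352×0.3384 + 0.0350 = 0.101
- q = 20%: 0.3928×0.0792 + 0.1836×0.4119 + 0.0596 = 0.166

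The last figure depends slightly on where the three patients fall. At q = 20% the splits 3+0, 2+1, 1+2 and 0+3 give 0.1682, 0.1663, 0.1620 and 0.1532. If the three are placed at random, the weights are 286, 546, 273 and 35 out of 1,140. The average is 0.165, the figure used below. The averages at q = 0, 5% and 10% stay at 0.049, 0.074 and 0.101.

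**Step 3: vary m.** False-positive chance, with the other patients at 5% (stage 1 + stage 2 splits 1+0, 1+1, 2+1, 3+1):

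| m | q = 0 | 5% | 10% | 15% | 25% |
|---|---|---|---|---|---|
| 1 | 6.5% | 7.4% | 8.3% | 9.2% | 11.0% |
| 2 | 5.7% | 7.4% | 9.1% | 11.0% | 15.1% |
| 3 | 4.9% | 7.4% | 10.1% | 13.2% | 20.3% |
| 4 | 4.2% | 7.4% | 11.2% | 15.6% | 26.0% |

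**Step 4: the price of counting them as not improved.** With the other patients at 25% and q = 0, power is 88.1%, 85.9%, 82.9% and 79.3% for m = 1 to 4, against 90.3% with complete week-9 data.

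**The case against.** The strongest reply is that the week-3 MRI is scheduled for every patient, the fallback is fixed in advance, and the alternatives are no cleaner. Mayo level is to be read from MRI and CT together, with MRI read at a single site for consistency and CT read locally (Protocol 5.2.11). A post-treatment CT alone may come well after the drug was stopped. This stands as a reason not to make that CT the automatic replacement.

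A reader might infer that whenever week 9 is missing, the SAP passes over a later scan that the protocol demands. The text does not support that. The post-treatment CT is a recommendation, covers only permanent removal for intolerable toxicity, and is later than week 3 only if the patient stopped after the week-3 scan.

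A reader might also infer that week-9 scans will be missing mainly because of toxicity, progression or death. Neither document says so. Protocol 5.3 keeps discontinued patients in efficacy follow-up, so some may still have a week-9 scan. Patients whose thrombus extends are expedited to surgery (Protocol 3.4, SAP 5.2). If the week-3 scan shows the extension, the fallback scores them as deteriorated.

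Two existing provisions help in part. SAP 7.5.3 lists Mayo level at screening, week 3 and week 9, so a level-based success resting on week 3 can be found by hand. The listing does not include the level 0 sub-level criterion and commits nobody to a recount. SAP 8.1 says multiple imputation will be considered above 10% missing; 3 of 20 is 15%. It does not say whether a patient with a week-3 substitute counts as missing.

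Last, the week-3 scan can also miss a response that comes later, so the rule does not favour the drug in every case. That is correct.

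**Conclusion.** The point holds as a weakness in one scoring rule and in the sensitivity analysis around it. A week-3 improvement counts as a week-9 success, and nothing planned shows whether the verdict depends on it. Against true week-9 status the direction is unknown. Only in comparison with counting these patients as not improved is it one-way: the rule can add successes and never remove them.

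The size is illustrative. With three fallback patients and 5% in the rest, the false-positive chance is 4.9%, 7.4%, 10.1% or 16.5% as *q* is 0, 5%, 10% or 20%. A reader might infer that the trial's error rate exceeds its 10% limit. The documents do not support that: it needs week-3 improvement to be more likely in these patients than the 5% null rate, and at 5% the error equals the design's own 7.4%. The two-stage design itself is sound. This is a cheap improvement.

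**What to change.** In SAP 7.6.1:

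1. Add a sensitivity analysis of the primary endpoint in which every evaluable patient without a week-9 reading counts as not improved.
2. Report how many successes rest on a week-3 scan, including those under the level 0 criterion, and state whether the three-patient verdict still holds without them.
3. State that where a pre-surgical scan later than week 3 exists, and can be read for Mayo level against the same modality at screening, it is used in preference to week 3. Flag any reading based on CT alone.
4. Say how this rule fits with the multiple imputation mentioned in SAP 8.1.

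The cost is SAP wording, one re-tabulation and a Mayo reading of a few scans already taken. Visits, treatment and sample size do not change. The not-improved count is conservative: with three such patients, power is about 83% instead of 90%. It therefore belongs as a sensitivity analysis and not as the primary analysis. A few readings may rest on CT alone.
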